5.4. Patient withdrawal

If the patient was not administered at least one dose of the investigational product and left the study for any reason, then further monitoring is not carried out, and data of this patients are not included in the statistical analysis.

Unless the patient withdraws consent, those who discontinue study drug early should remain in the study, if possible, for further acquisition of endpoint measurements. The reason for patient discontinuation of study drug should be documented in the case report form.

The investigator submits the data on the patients excluded from the study to the Sponsor and the monitor of the study within 24 hours in the form of a report that includes the patient's status at the end of the study.

Patient status at the end of the study:

1. *Completed the study.*
2. *Did not complete the study because of:*
 - The investigator's mistake.
 - Adverse events.
 - Serious adverse events.
 - Pregnancy.
 - Protocol violations.
 - The patient's wish to leave the study.
 - The patient did not show up for a visit.
 - Other reasons (specify).

5.5. Replacement of the subjects

This study does not provide for the replacement of withdrawn study participants.

5.6. Follow up of the withdrawn patients

The subjects that were withdrawn from the study because of an AE/SAE will be followed until the AE/SAE is resolved or the patient is stabilized.

5.7. Strategies for Recruitment and Retention

5.7.1. Screening

It is anticipated that patients with COVID-19 will present to participating hospitals, and that no other efforts to recruit potential subjects are needed. Recruitment efforts may also include spreading information about this study among other medical professionals / hospitals.

Patients that are confirmed to have SARS-CoV-2 will be assessed for eligibility.

Some patients will not be included in the study based on demographic data and medical history, namely, due to pregnancy, age under 18 years, and so on. Potential participants will be told about the study and asked questions to determine if they can be included in the study. The study procedures can begin only after informed consent is obtained.

5.7.2. Retention

Participating subjects will be reminded of subsequent visits.

6. STUDY PLAN

6.1 Schedule of the study visits and procedures

The study will be conducted in the clinical centre during hospitalization and outpatient visits of patients who were discharged by their attending physician according to routine clinical

practice.

The study will include the following periods:

Treatment period (17 days in total, days 1...17) with administration of the investigational product (intravenous injections for 3 days, then intramuscular injections for 14 days), assessment of the clinical status, recording of AEs.

Follow-up period (days 18...29±3)

Additional visits can be performed if judged necessary by the study doctor. The study doctor will define the scope of assessments and procedures for the additional visits individually, based on the patient's needs.

The Early Termination Visit is performed if the patient is withdrawn from the study. The scope of activities and procedures carried out at the visit is similar to the activities and procedures carried out at the visit on Day 29.

Schedule of the study procedures is included in the Appendix 1.

6.2. Description of the visits

A comprehensive description of visits (by days) is provided in Appendix 1. All procedures described below should be carried out as part of the routine practice of the health care institution.

Preliminary evaluation of the inclusion/exclusion criteria

(Before the study initiation)

Full list of the procedures is provided in Appendix 1.

- Signing of informed consent.
- Confirmation of the positive test for SARS-CoV-2¹.
- Collection of patient history, demographics, and anthropometric data.
- Collection of information about previous/concomitant treatments.
- Physical examination (including lung auscultation).
- Evaluation of chest X-ray or CT scans².
- Laboratory test³: haematology, biochemistry, urinalysis.
- Oxygen saturation (SpO₂).
- Evaluation of the eligibility.

Treatment period

Day 1 - enrolment, initiation of the treatment

Full list of the procedures is provided in Appendix 1.

- Evaluation of measures of clinical support.
- Assessment of the clinical status according to the 7-point ordinal scale.
- Assessment of the clinical status according to the NEWS scale and SOFA scale.
- Oropharyngeal/nasal (OP/N) sample.
- Haematology (only if this test was not performed at the screening).
- Blood chemistry (only if this test was not performed at the screening).
- Urinalysis (only if this test was not performed at the screening).
- Administration of the investigational product
- Physical examination (including lung auscultation).
- Collection of the efficacy data (oxygenation, mechanical ventilation, prolongation of

¹ Data obtained not later than 48 hours before signing the informed consent may be used.

² Recent chest X-ray/CT scans can be used, if the scans were obtained after the coronavirus disease (COVID-19) was diagnosed.

³ If the patient has results of laboratory tests that were performed within 48 before the enrolment, these results can be used to assess the clinical status and eligibility. These data can be used only if they are complete and include all parameters specified in the Protocol. Repeated laboratory tests on Visit 0 are not required in this case.

hospitalization).

- Recording of AEs.

Days 2...18

Full list of the procedures is provided in Appendix 1.

The visits are performed in the in-patient settings. If the patient is discharged before Day 17, the procedures will be performed at the outpatient visits to the clinic.

Visits to the clinic are preferred after discharge, but the quarantine or other reasonable factors can limit this opportunity. The visits could be performed in a form of phone call or with other remote communication technologies. Some data will not be collected by obvious reasons.

- Evaluation of the measures of clinical support.
- Assessment of the clinical status according to the 7-point ordinal scale — every day during hospitalization up to and including Day 17.
- Assessment of the clinical status according to the NEWS scale and SOFA scale.
- Oropharyngeal/nasal (OP/N) sample.
- Haematology.
- Blood chemistry.
- Urinalysis.
- Administration of the investigational product.
- Physical examination (including lung auscultation).
- Collection of the efficacy data (oxygenation, mechanical ventilation, prolongation of hospitalization).
- Collection of information about concomitant treatments.
- Recording of AEs.

Follow-up period

(Day 29±3)

Full list of the procedures is provided in Appendix 1.

The visits are performed in the in-patient settings. If the patient is discharged earlier, the procedures will be performed within the outpatient visits to the clinic (if possible).

- Evaluation of the measures of clinical support — only if the hospitalization is prolonged.
- Assessment of the clinical status according to the 7-point ordinal scale.
- Assessment of the clinical status according to the NEWS scale and SOFA scale.
- Oropharyngeal/nasal (OP/N) sample.
- Haematology.
- Blood chemistry.
- Urinalysis.
- Collection of the efficacy data (oxygenation, mechanical ventilation, prolongation of hospitalization).
- Collection of information about concomitant treatments.
- Physical examination (including lung auscultation).
- Recording of AEs.

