4. STUDY DESIGN

4.1. Primary and Secondary Outcomes

According to the aim and objectives of this study, safety and efficacy of Polyoxidonium®, lyophilizate for solution for injections and topical application, 6 mg (NPO Petrovax Pharm LLC, Russia) will be evaluated in hospitalized patients with coronavirus disease (COVID-19).

Efficacy outcomes

Primary efficacy outcome

Subject clinical status using the WHO 7-point ordinal scale on day 15 as compared to baseline.

1. Not hospitalized, no limitations on activities.
2. Not hospitalized, limitation on activities.
3. Hospitalized, not requiring supplemental oxygen.
4. Hospitalized, requiring supplemental oxygen.
5. Hospitalized, on non-invasive ventilation or high flow oxygen devices.
6. Hospitalized, on invasive mechanical ventilation or ECMO.
7. Death.

Secondary efficacy outcomes

Clinical severity assessed by scales

1. Subject clinical status using the WHO 7-point ordinal scale

- Time to improvement of each parameter of the primary scale from admission.

- Subject clinical status at days 3, 5, 8, 11, and 29.
 - Average change in the clinical status at days 3, 5, 8, 11, 15, and 29 as compared to baseline.
2. *The NEWS Score (National Early Warning Score) describes the vital signs (pulse rate, breathing rate, temperature, blood pressure etc.) and its deviation from the reference ranges):* is evaluated daily and on day 15.
- The time to discharge or to a NEWS of ≤ 2 and maintained for 24 hours, whichever occurs first.
 - Change from baseline to days 3, 5, 8, 11, 15, and 29 in NEWS.
3. *Oxygenation, including mechanical ventilation:*
- Change (day by day) in the need for oxygenation in the first 28 days (up to day 29).
4. *Hospitalization*
- Duration of hospitalization (days).
5. *Mortality (date, cause)*
- 28-day mortality.
6. *SOFA scale (evaluation of organ failure associated with sepsis):* is evaluated daily and on day 15.
- Change from baseline to days 3, 5, 8, 11, 15, and 29 in SOFA.

Safety outcomes

Safety outcomes

- Cumulative incidence of serious adverse events/reactions (SAEs, SARs)
- Cumulative incidence of adverse events/reaction (AEs, ARs)
- Permanent or temporary discontinuation of infusions/injections (by any cause)
- Clinically significant changes in the levels of leukocytes, haemoglobin, platelets, creatinine, glucose, total bilirubin, ALT, AST, CRP, and other parameters.

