9.4. Drop-outs, withdrawn patients, and missing data

No missing data will be substituted. The missing/omitted data will not be considered during statistical analysis.

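### Late NEWS and SOFA changes may over-represent patients still in hospital and leave out deaths, because values not measured after discharge or death are dropped

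*Combined protocol and SAP*

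**What the plan says.** Section 4.1 lists two secondary outcomes at fixed days: "Change from baseline to days 3, 5, 8, 11, 15, and 29 in NEWS" and "Change from baseline to days 3, 5, 8, 11, 15, and 29 in SOFA".

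Section 6.2 sets out what happens once a patient goes home. For the treatment period the default is in person: "If the patient is discharged before Day 17, the procedures will be performed at the outpatient visits to the clinic". It then relaxes this. "Visits to the clinic are preferred after discharge", but quarantine or other factors may prevent them, and "The visits could be performed in a form of phone call or with other remote communication technologies". It adds that "Some data will not be collected by obvious reasons", without naming the data. The notes to Table 1 repeat this. For Day 29 the commitment is weaker: "the procedures will be performed within the outpatient visits to the clinic (if possible").

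Section 6.3.8 builds NEWS from seven parameters, including respiration rate, oxygen saturation, temperature, systolic pressure and heart rate. The hospital chart is the only source it names. It describes SOFA as an organ-failure scale for intensive care but does not list its components.

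Section 9.4 gives the whole missing-data rule: "No missing data will be substituted. The missing/omitted data will not be considered during statistical analysis". No section says what NEWS or SOFA value a discharged or deceased patient contributes.

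**The concern.** Most missing-data problems depend on how many patients happen to drop out. Here the mechanism is built into the schedule. A patient who recovers goes home and may be followed by phone, so has no NEWS. A patient who dies has no NEWS. A patient who stays in hospital is scored daily. Under 9.4 the first two groups leave the calculation for that day, and each day's mean change is taken over a different, outcome-selected subset.

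Losing recovered patients makes the average look worse, and losing deaths makes it look better. The net error has no predictable sign, and a reader of the report could not recover it, because the plan does not ask for numbers measured by day or visit type.

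Two other provisions add to this. Section 9.7.2.2 plans repeated-measures ANOVA and the Friedman test. In standard form both need complete series, so a missing late score can also remove a patient's earlier days. Section 11.8 lists a missed visit among significant deviations and excludes such patients from the final efficacy analysis. That conflicts with the ITT population in 9.6 and 9.7.2.

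**Working it through.** There is no plan figure to reproduce. The documents give a sample size of at least 50 and no discharge rate, death rate, expected clinic attendance or NEWS distribution. The check is arithmetic on who is observed, with assumed inputs shown over a range.

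**Step 1: size at Day 15, survivors as reference.** Assumptions: of 50 patients, 32 are discharged (NEWS 4 to 1, change -3), 13 are in hospital (6 to 4, change -2) and 5 are dead. If *a* discharged patients attend the clinic, and attenders resemble the other discharged patients:

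observed change = [*a*(-3) + 13(-2)] / (*a* + 13); observed NEWS = [*a*(1) + 13(4)] / (*a* + 13)

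| Attendance of the 32 | Observed n | Inpatient share | Mean NEWS | Mean change |
|---|---|---|---|---|
| 0% (0) | 13 | 100% | 52/13 = 4.0 | -26/13 = -2.0 |
| 25% (8) | 21 | 62% | 60/21 = 2.9 | -50/21 = -2.4 |
| 50% (16) | 29 | 45% | 68/29 = 2.3 | -74/29 = -2.55 |
| 100% (32) | 45 | 29% | 84/45 = 1.9 | -122/45 = -2.7 |

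The shortfall in mean change against all survivors is 0.7 points at no attendance, about 0.3 at 25% and about 0.2 at 50%. The 5 deaths are absent from every row.

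**Step 2: when inpatients form the majority.** With *d* the share discharged and *c* the share of those seen in person (deaths ignored), the inpatient share of observed values is (1-*d*) / [(1-*d*) + *d c*]. It exceeds one half only if *c* < (1-*d*)/*d*. The threshold for *c* is 100% at *d* = 0.5, 43% at 0.7, 25% at 0.8 and 11% at 0.9.

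**Step 3: direction.** Take *d* = 0.8, 10% dead and 10% in hospital. Assume changes of -4 in discharged patients, -1 in inpatients and, for illustration only, +6 for a death. The whole-cohort mean is 0.8(-4) + 0.1(-1) + 0.1(6) = -2.7. The observed means are:

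- *c* = 0: -1.0, so improvement is understated.
- *c* = 0.25: [0.2(-4) + 0.1(-1)] / 0.3 = -3.0, so improvement is overstated.
- *c* = 0.5: [0.4(-4) + 0.1(-1)] / 0.5 = -3.4, so it is overstated further.

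The sign of the error reverses within one scenario as attendance changes.

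**Step 4: which days.** Table 1 schedules doses on Days 11 and 15, so a discharged patient still on treatment has a reason to be seen. Day 29 has no dose and the weaker clinic commitment. Day 8 is an endpoint day but not a dosing day. Table 1 has a column for Days 3, 5, 7 and 11 instead, so a Day 8 score falls only under its daily-until-discharge column, although section 6.2 covers Days 2 to 18 in general terms.

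**The case against.** The strongest reply is that in-person visits are the default and phone contact the fallback, so many discharged patients may be measured, especially on Days 11 and 15. This stands in part. It reduces the expected loss on those days and rules out treating 0% attendance as the likely case. It does not remove the problem. Section 6.2 puts drug administration in the same list of visit procedures that may become a phone call, and on Day 29 neither safeguard applies.

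A second reply is that discharge and death are captured elsewhere: in the 7-point scale, the time to discharge or low NEWS, the duration of hospitalization and 28-day mortality. That is correct. Those endpoints are much less exposed, and the point is confined to secondary, single-group summaries.

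A third is that section 4.3 acknowledges withdrawal bias and section 9.10 has a sensitivity check. Neither reaches this. Discharge is not withdrawal, and 9.10 concerns data errors that cannot be corrected.

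For SOFA, the documents list no components. That it cannot be scored by phone is an inference from its description; for NEWS it follows from the table in 6.3.8.

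A reader might infer that the Day 11 to 29 changes describe mainly patients still in hospital, or say nothing about the enrolled population. The documents do not support either. The first needs attendance below the Step 2 thresholds, and no attendance figure is given. On the second, the error is modest in Step 1 once half the discharged patients attend.

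**Conclusion.** The point holds in this form. Followed as written, sections 6.2 and 9.4 let discharge and death decide who is included in the later NEWS changes and, by inference, the SOFA changes. These may over-represent inpatients and they omit deaths, by an amount the documents do not allow anyone to fix and in either direction. The risk is greatest at Day 29 and smaller on Days 11 and 15.

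On the assumed Day 15 figures the observed change runs from -2.0 (no attendance) through -2.4 (25%) to -2.55 (50%), against -2.7 in all survivors, with 5 of 50 patients missing throughout because they died. Those sizes rest on assumed patient splits and scores, and on attenders resembling non-attenders among the discharged. The selection itself does not depend on those figures. The change should be made, but the primary endpoint is not at issue here.

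**What to change.** For NEWS and SOFA at fixed days, replace the 9.4 rule with the following:

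- Use the measured value whenever one exists, including clinic values after discharge.
- Give deaths the worst rank, which matches the place of death on the 7-point scale.
- Only for patients discharged alive with no measurement that day, use the last in-hospital value.
- Analyse by the Wilcoxon signed-rank test already named in 9.7.2.2, whatever the normality test shows, because a worst rank has no numerical mean.
- Report the number measured by day and by visit type (inpatient, clinic, remote).
- Keep the observed-only mean as a sensitivity analysis.

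In section 11.8, state that a missed or remote visit after discharge does not trigger exclusion from the efficacy analysis, so that the ITT population in 9.6 and 9.7.2 holds. Settle this before the data are examined, since 9.3 and 9.7 allow methods to be replaced or chosen later.

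The cost is a wording change to 9.4, 9.7.2.2 and 11.8, made as a written amendment under 11.7, and a visit-type field in the eCRF if there is none. No extra patients or procedures are needed. The downside is that carry-forward assumes unmeasured discharged patients do not worsen, which is least secure at Day 29. The counts by visit type show how far the result leans on it.

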6.3. Study procedures

6.3.1. Written informed consent

The patient should sign two copies of the Patient Information Leaflet and the Informed Consent Form for participation in this study before any initiation of any study procedures.

The patient should receive the written information about:

1. The drug product for human use and nature of this observational study.
2. Safety of the drug product for human use and risks for the patient.

3. Terms of participation in the observational study of the drug product for human use.
4. Aim, objectives, and duration of the observational study of the drug product for human use.
5. Patient actions in case of unexpected effects of the drug product for human use on the patient's health.
6. Confidentiality statement in relation to participation in the clinical study of the drug product for human use.

The Investigator should also sign and date the Patient Information Leaflet and the Informed Consent Form and hereby confirm that the study was discussed with the patient and the patient gave his/her consent, that the patient had the opportunity to ask questions and received full answers to all questions.

The patient will receive one copy of the Patient Information Leaflet and the Informed Consent Form. The second copy will be kept by the investigator in the study centre together with the other clinical study records.

6.3.2. Collection of the patient history

During the screening, the patient's detailed medical history will be collected, in particular, diseases transferred over the last year, concomitant diseases, previous surgery, previous (over the last 4 weeks) and concomitant therapy, history of alcohol, drugs and / or drugs addictions, information about bad habits (smoking and drinking), including the following:

- Day of onset of COVID-19 symptoms
- History of chronic medical conditions related to inclusion and exclusion criteria
- Medication allergies
- List of medications and therapies for this current illness

6.3.3. Collection of demographic and anthropometric data

Demographic and anthropometric data (date of birth, gender, race) will be collected during the enrolment.

6.3.4. Physical examination

The physical examination will be carried out by the study doctor in accordance with the schedule of the study procedures outlined in Appendix 1.

The examination includes¹:

- Lung auscultation and percussion.
- Assessment of the visible mucous membranes of the upper respiratory tract.
- Palpation of lymph nodes.
- Examination of the abdominal organs and size of the liver and spleen (without instrumental investigation, by palpation; criteria for assessing the size of the liver and spleen: increased / not increased).
- Measurement of the body temperature.

6.3.5. Laboratory tests

The schedule of laboratory tests is included in description of the study parts and in the schedule of the study procedures.

List of the evaluated laboratory parameters

¹ Temporary guidelines. Prevention, diagnosis, and treatment of the novel coronavirus infection (2019-nCoV). Version 2 (02/03/2020). Electronic source with free access: <https://static-i.rosminzdrav.ru/system/attachments/attaches/000/049/329/original/%D0%92%D1%80%D0%B5%D0%BC%D0%B5%D0%BD%D0%BD%D1%8B%D0%B5%D0%9C%D0%A0%2019-nCov%2003.02.2020%28%D0%B2%D0%B5%D1%80%D1%81%D0%B8%D1%8F%29%29%20final.pdf?1580748451>.
Access date: March 16, 2020.

Haematology

Red blood cells, haematocrit, white blood cells, platelets, neutrophils, eosinophils, basophils, monocytes, lymphocytes

The volume of the blood sample is approximately 5 mL.

Blood chemistry

Urea, creatinine, Na⁺, K⁺, bilirubin, glucose, ALT, AST, albumin, pH, bicarbonates, lactate, coagulogram with prothrombin time, coagulogram with international normalized ratio and activated partial thromboplastin time, CRP. The blood sample volume is approximately 5 mL.

If indicated: PaO₂, FiO₂, PaCO₂

Urinalysis

According to routine practice of the centre.

Test for SARS-CoV-2

The test is performed at the screening to assess the eligibility. Data obtained not later than 48 hours before signing the informed consent may be used.

Oropharyngeal/nasal (OP/N) sample

Oropharyngeal/nasal samples will be taken in accordance with the routine practice of the health care institution.

6.3.6. Evaluation of chest X-ray or CT scans

The scans are evaluated before the enrolment¹. Recent chest X-ray/CT scans (frontal view and lateral view) will be used, if the scans were obtained after the coronavirus disease (COVID-19) was diagnosed.

6.3.7. Oxygen saturation (SpO₂)

This assessment is performed before the enrolment according to the schedule of study procedures.

6.3.8. Collection of efficacy data

The efficacy data (the need for oxygenation, the need for mechanical ventilation, continued hospitalization) will be collected daily during the study to assess the effectiveness of therapy during hospitalization. The selected scales are recommended for efficacy assessment by WHO².

The patient status will also be assessed using the following questionnaires/scales in accordance with the description of the study periods and the schedule of the study procedures.

Examples of the scales used in the study

¹ Temporary guidelines. Prevention, diagnosis, and treatment of the novel coronavirus infection (2019-nCoV). Version 2 (02/03/2020). Electronic source with free access: <https://static-i.rosminzdrav.ru/system/attachments/attaches/000/049/329/original/%D0%92%D1%80%D0%B5%D0%BC%D0%B5%D0%BD%D0%BD%D1%8B%D0%B5%D0%9C%D0%A0%2019-nCov%2003.02.2020%28%D0%B2%D0%B5%D1%80%D1%81%D0%B8%D1%8F%2029%20final.pdf?1580748451>. Access date: March 16, 2020.

² MASTER PROTOCOL. A Multi-centre, Adaptive, Randomized, Double-Blind, Placebo-Controlled Clinical Trial of the Safety and Efficacy of Investigational Therapeutics for the Treatment of COVID-19 in Hospitalized Patients. Electronic source with free access: <https://www.who.int/blueprint/priority-diseases/key-action/multicenter-adaptive-RCT-of-investigational-therapeutics-for-COVID-19.pdf>. Access date: March 13, 2020

Measures of clinical support

The following measures of clinical support will be evaluated on each day of hospitalization up to day 17:

- Hospitalization
- Oxygen requirement
- Non-invasive mechanical ventilation (via mask)
- Mechanical ventilator requirement (via endotracheal tube or tracheostomy tube)
- ECMO requirement

7-point ordinal scale

Recommended by WHO as the primary endpoint for evaluating the efficacy of coronavirus infection therapy¹.

The 7-point ordinal scale is an assessment of the clinical status at the first assessment of a given study day. Each day, the worse score for the previous day will be recorded. For example, on day 3, day 2 score is obtained and recorded as day 2. The scale is as follows:

1. Not hospitalized, no limitations on activities.
2. Not hospitalized, limitation on activities.
3. Hospitalized, not requiring supplemental oxygen.
4. Hospitalized, requiring supplemental oxygen.
5. Hospitalized, on non-invasive ventilation or high flow oxygen devices.
6. Hospitalized, on invasive mechanical ventilation or ECMO.
7. Death.

NEWS Score

This score is based on 7 clinical parameters. The NEWS scale is used to evaluate efficacy and is recommended by WHO².

Literature shows that the NEWS score allows discriminating patients at risk of adverse outcomes [Smith et al., 2016].

This should be evaluated at the first assessment of a given study day. These parameters can be obtained from the hospital chart using the last measurement prior to the time of assessment. This is recorded for the day obtained. For example, on Day 3, Day 3 score is obtained and recorded as Day 3.

Physiological parameters	3	2	1	0	1	2	3
Respiration rate	≤8		9–11	12-20		21 -24	≥25
Oxygen saturation	≤91	92-93	94-95	≥96			

¹ WHO R&D Blueprint novel Coronavirus COVID-19 Therapeutic Trial Synopsis. Electronic source with free access: https://www.who.int/blueprint/priority-diseases/key-action/COVID-19_Treatment_Trial_Design_Master_Protocol_synopsis_Final_18022020.pdf. Access date: March 20, 2020.

² MASTER PROTOCOL. A Multi-centre, Adaptive, Randomized, Double-Blind, Placebo-Controlled Clinical Trial of the Safety and Efficacy of Investigational Therapeutics for the Treatment of COVID-19 in Hospitalized Patients. Electronic source with free access: <https://www.who.int/blueprint/priority-diseases/key-action/multicenter-adaptive-RCT-of-investigational-therapeutics-for-COVID-19.pdf>. Access date: March 13, 2020

Physiological parameters	3	2	1	0	1	2	3
Any Supplemental Oxygen		Yes		No			
Temperature	≤35.0		35.1-36.0	36.1-38.0	38.1-39.0	≥39.1	
Systolic BP	≤90	91-100	101-110	111-219			≥220
Heart Rate	≤40		41-50	51-90	91-110	111-130	≥131
Level of Consciousness				A			V, P, or U

Level of consciousness = alert (A), and arousable only to voice (V) or pain (P), and unresponsive (U).

SOFA Score

The SOFA scale is used to evaluate the clinical state and is recommended by WHO. Moreover, the SOFA scale was chosen because it is widely known, simple and applicable to most hospital settings. It was developed by the Sepsis Task Force of the European Society of Critical Medicine.

SOFA Organ Deficiency Assessment (Sepsis-related Organ Failure) is a point scale for assessing multiple organ failure in patients with septic syndrome who are in intensive care. This scale was created to quickly calculate and describe a number of complications in critically ill patients. The scale is intended rather for quick scoring and description of a number of complications than for predicting the outcome.

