16. APPENDICES

SCHEDULE OF ASSESSMENTS

Table 1. Study plan
(ALL THESE PROCEDURES SHOULD BE CARRIED OUT IN THE FRAMEWORK OF ROUTINE PRACTICE OF THE HEALTH CARE INSTITUTIONS)

Procedure / days	Study according to the Protocol No. COVID dated March 30, 2020				
	Day 1	Daily (up to discharge ^{***})	Day 3, 5, 7, 11	Day 15±1	Day 29±3 or any other last day ^{****} of the study
Enrolment criteria	X				
Withdrawal criteria		X	X	X	X
Informed consent, enrolment	X				
Polyoxidonium	10 doses: days 1, 2, 3, 5, 7, 9, 11, 13, 15, 17				
History	X				
Clinical signs and symptoms, physical examination¹	X	X	X	X	X
Nasopharyngeal and/or oropharyngeal smear	X		X	X	X
Haematology²	X**		X	X	X
Blood chemistry³	X**		X	X	X
CRP	X**		X	X	X
Urinalysis⁴	X**		X	X	X
Bacteriological inoculation of sputum	If necessary				
Chest X-ray/ CT*	If indicated				
ECG*	If indicated				
SpO₂⁵	X	X	X	X	X
Evaluation of need for oxygenation, including mechanical ventilation	X	X	X	X	X
Assessment of the treatment efficacy⁶	X	X	X	X	X
Assessment of safety	X	X	X	X	X
NEWS Score	X	X	X	X	X
SOFA Score	X	X	X	X	X
Clinical status by WHO scale	At admission	X	X	X	X

Notes to Table 1

*- including at admission, before enrolment

** - results of the previous laboratory investigations within 48 hours before enrolment can be used

*** - visits to the clinic are preferred after discharge, but the quarantine or other reasonable factors can limit this opportunity. The visits could be performed in a form of phone call or with other remote communication technologies. Some data will not be collected by obvious reasons.

**** - in case of the patient withdrawal (see the withdrawal criteria)

1 – Clinical signs and symptoms

Weakness, fatigue, cough, shortness of breath, stuffiness in the chest, myalgia, headaches, haemoptysis, palpitations, nasopharyngeal symptoms, diarrhoea, nausea, vomiting; physical

examination: heart rate, blood pressure, respiratory rate, body temperature

2 – Haematology

Red blood cells, haematocrit, white blood cells, platelets, neutrophils, eosinophils, basophils, monocytes, lymphocytes

3 - Blood chemistry

Urea, creatinine, Na⁺, K⁺, bilirubin, glucose, ALT, AST, albumin, pH, bicarbonates, lactate, coagulogram with prothrombin time, coagulogram with international normalized ratio and activated partial thromboplastin time, CRP

If indicated: PaO₂, FiO₂, PaCO₂

4 – Urinalysis

According to routine practice of the centre

5 - SpO₂

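### The protocol gives two different end dates for daily recording of oxygen support and WHO status, Day 17 and discharge, while a secondary endpoint needs daily oxygenation status for 28 days

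*Combined protocol and SAP*

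**What the plan says.** Section 4.1 (repeated in the synopsis and section 7.1) defines the oxygenation endpoint as "Change (day by day) in the need for oxygenation in the first 28 days (up to day 29". It also lists time to improvement on the WHO 7-point scale as a secondary outcome.

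Two places stop daily recording at Day 17:
- Section 6.3.8, on hospitalization, oxygen, non-invasive and invasive ventilation and ECMO: "The following measures of clinical support will be evaluated on each day of hospitalization up to day 17".
- Section 6.2, on the WHO scale: "every day during hospitalization up to and including Day 17". This bullet stands under a heading that runs to Day 18. After that, section 6.2 describes only the Day 29±3 visit, although section 6.1 defines a "Follow-up period (days 18...29±3").

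Two places set no such limit:
- The opening sentence of section 6.3.8: "The efficacy data (the need for oxygenation, the need for mechanical ventilation, continued hospitalization) will be collected daily during the study", for the time in hospital.
- Table 1 in section 16, whose daily column is headed "Daily (up to discharge"). The rows "Evaluation of need for oxygenation, including mechanical ventilation" and "Clinical status by WHO scale" are both marked in that column, as are SpO₂, NEWS and SOFA.

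Two further rules matter. Under section 6.3.8 the WHO score entered on a given day is the worse score of the day before. Under section 9.4 missing data are neither imputed nor considered in the analysis.

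**The concern.** A day-by-day endpoint over 28 days needs a value for each day. The items listed in section 6.3.8 are the direct inputs to it, and the WHO scale is the input to time to improvement. If recording stops at Day 17, patients who are still in hospital then, whose later course the 28-day window is meant to capture, lose those inputs until the follow-up visit. Section 9.4 then leaves the days out.

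Because the study has several centres, one centre can stop at Day 17 and another can continue to discharge, and both can say that they followed the protocol. The late part of the oxygenation curve would then depend partly on which sentence each centre read. The sample is at least 50 patients, so few may still be in hospital that late, and each lost record would count.

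**Working it through.** The plan states no figure for this point, so the check is a day count under each rule.

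**Inputs**
- Endpoint window: 28 days, taken as Days 1 to 28 (section 4.1).
- Last day of daily recording: Day 17 (section 6.3.8 list; section 6.2 for the WHO scale), Day 18 (heading in section 6.2, under which collection of oxygenation data is also listed), or discharge (Table 1).
- Follow-up visit: Day 29±3, so Day 26 to Day 32.

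**Endpoint days without daily recording, for a patient in hospital throughout**

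Formula: gap = 28 − last day recorded; share = gap / 28.

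| Rule that governs | Days covered | Gap | Share |
|---|---|---|---|
| Day 17 wording | 17 (17/28 = 60.7%) | 28 − 17 = 11 (Days 18–28) | 11/28 = 39.3% |
| Day 18 heading in section 6.2 | 18 | 28 − 18 = 10 (Days 19–28) | 10/28 = 35.7% |
| Table 1, or opening of section 6.3.8 | 28 | 0 | 0% |

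The gap is shorter for a patient who leaves hospital before Day 28. It falls by one day if the follow-up visit is on Day 26, 27 or 28.

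**Unobserved run from Day 18 to the day before the follow-up visit**

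Formula: run = visit day − 18.
- Visit on Day 26: 26 − 18 = 8 days.
- Visit on Day 29: 29 − 18 = 11 days.
- Visit on Day 32: 32 − 18 = 14 days, of which 11 lie within Days 18 to 28.

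**Scoring lag.** The 11 days take Day 17 as the last day scored. If Day 17 is instead the last day on which a WHO score is entered, the last score is for Day 16 and the WHO gap is 28 − 16 = 12 days (12/28 = 42.9%). The documents do not say which is meant.

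**What other records still date**
- Moves to WHO categories 1 and 2 are discharges, which are dated through duration of hospitalization.
- Category 7 is death, and mortality is recorded with its date.
- NEWS is evaluated daily (section 4.1) and has a yes/no item for supplemental oxygen. It can date a change between oxygen and no oxygen, but not a step between invasive ventilation, non-invasive or high-flow support and ordinary oxygen.

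So the steps at risk are those between support levels in hospital, on Days 18 to 28, at sites that follow the Day 17 wording.

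**After discharge.** Table 1 ends daily recording at discharge. Its notes allow remote visits and accept that some data will not be collected. No rule assigns oxygen need to the remaining days up to Day 28, whichever end date governs.

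**The case against.** The strongest reply is that Table 1 governs. Section 6.2 refers to Appendix 1 for the comprehensive description of visits and, under each period, for the full list of procedures. The opening sentence of section 6.3.8 names the oxygenation and ventilation variables and has no Day 17 limit. On that reading the two Day 17 clauses are slips and no inpatient data are lost.

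Much of this stands. It rules out a stronger reading that the Day 17 clauses invite: that daily recording is specified only to Day 17, so that Days 18 to 28 go unobserved and 39% of the endpoint is missing. Table 1 and the opening of section 6.3.8 both contradict that. A reader might also infer that any improvement after Day 17 can be dated only to the follow-up visit, 11 or even 14 days late. That fails too, because discharge and death carry their own dates and NEWS carries an oxygen item. Nor do the documents give any length-of-stay figures from which to estimate how many patients would be affected.

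The reply does not remove the conflict. Section 6.3.8 ties the scales both to the description of the study periods and to the schedule of procedures, and these two sources give different end dates. Section 6.3.8 also disagrees with itself. A site that stops the itemised list at Day 17 is following an explicit instruction.

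**Conclusion.** The documents contradict each other on when daily recording ends, and the contradiction bears on a stated secondary endpoint. The size is conditional: up to 11 of 28 days (39%) without an itemised support record or WHO score, for a patient still in hospital, if the Day 17 wording is followed; zero for inpatients if Table 1 is followed. This assumes that the window is Days 1 to 28 and that Day 17 is the last day scored. The number of patients affected cannot be estimated from the documents.

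The consequence is limited to steps between support levels in hospital after Day 17, together with the separate lack of a rule for days after discharge. The Day 15 primary endpoint is not affected. This is an inconsistency to be corrected, not a demonstrated loss of data.

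**What to change.** 1. Reconcile section 6.2, section 6.3.8 and Table 1. In both section 6.3.8 (support measures) and section 6.2 (WHO scale), replace the Day 17 limit by: *up to discharge, death or Day 28, whichever is first*. Carry the same daily recording for inpatients into the follow-up part of section 6.2.
2. Because each WHO score is entered the next day, state that the Day 28 score is entered on Day 29, so that recording does not in effect end with the score for Day 27.
3. State how days after discharge and deaths enter the day-by-day oxygenation endpoint, given that section 9.4 imputes nothing:
   - Discharged without oxygen: counted as not needing oxygen, unless readmission or oxygen use is reported.
   - Discharged on oxygen: counted as needing oxygen until a change is reported.
   - Death: its own worst state from the date of death, not missing.

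The cost is a wording change in two sections, a short analysis rule, and the transcription of oxygen and ventilation status that should already be in inpatient charts. No new procedure or visit is needed. The rule after discharge relies on asking about oxygen use and readmission at the contacts that are already planned.
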